- Cycle 5: follow cycle 1 procedures (except dose remains at 200mg/m²/day)
- Cycle 6: follow cycle 2 procedures

Cycle 6, day 28 marks the completion of the full 6 cycles of adjuvant TMZ per the standard of care. If there is no contraindication, TMZ may be discontinued at that time. If there is clinical cause, physicians may opt to continue TMZ therapy longer beyond the 6 cycles. Otherwise, TTField therapy alone will be continued for maintenance.

Maintenance TTField therapy (Long-Term Follow-up)

At the end of the adjuvant therapy, the subject will continue TTF treatment per the standard of care, and the study will follow clinical outcomes via the chart and by telephone as needed. It is recommended that the subject have a follow-up MRI, objective response assessments, physical exam, and medication review with their neuro-oncologist at least every 3 months during this time for up to 2 years. Refer to sections on evaluation of response and evaluation of pseudoresponse for criteria of assessments. Investigators at each site will document the date of confirmed progression on MRI scan and or death, and cause of death for every subject that

has been on treatment for at least 1 day (disease assessment/extend of measurable disease on imaging with clinical response or deterioration, when an MRI has been completed per standard care). Site study coordinators will review patient records at minimum every 6 months starting from the date of initial Trimodal therapy while patients remain on study to collect data on TTF compliance, treatment response, disease progression, and survival. This will provide the secondary outcomes that will be analyzed and reported at the close of the study.

Unscheduled Visit, anytime during the Study Period (Day 1-Day 106 ± 5 days)

An unscheduled visit may be used if the investigator feels they need to see the patient for a safety concern or an additional indicated exam that is outside of a specified protocol visit window. Any of the following may be completed, per investigator discretion, based on where the patient is currently in the study.

- MRI of the brain with and without contrast (transducer arrays will need to be removed/replaced for imaging)
- Vital signs: weight, temperature, pulse, respiration rate, and resting blood pressure
- Physical examination including neurologic exam, skin and scalp assessment

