Progression	Defined by any of the following: Greater than or equal to 25% increase in sum of the products of perpendicular diameters of enhancing lesions compared with the smallest tumor measurement obtained either at baseline (if no decrease) or best response, on stable or increasing doses of corticosteroids*; significant increase in T2/FLAIR nonenhancing lesions on stable or increasing doses of corticosteroids compared with baseline scan or best response after

	initiation of therapy* not cause by comorbid events (eg, radiation therapy, demyelination, ischemic injury, infection, seizures, post-operative changes, or other treatment effects); any new lesion; clear clinical deterioration not attributable to other causes apart from the tumor (eg, seizures, medication adverse effects, complications of therapy, cerebrovascular events, infection, and so on) or changes in corticosteroid dose; failure to return for evaluation as a result of death or deteriorating condition; or clear progression of non-measurable disease.
--	--

Evaluation of Pseudoprogression

Pseudoprogression is defined as worsening of the MRI lesions (enhancing lesion, T2/FLAIR hyperintense nonenhancing lesions) as a result of effects other than tumor growth. These can be the result of treatment effects from radiation, TTFields therapy, or chemotherapy, or changes in the steroid dose. Pseudoprogression is typically self-limited and suggests different clinical implications from true progression of the brain tumor. However, clinically and radiographically, pseudoprogression and tumor progression are difficult to distinguish.

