F: Confirmation of MRI completion within 3 days after tumor resection, with up to 5 additional days logistical delay being acceptable. If biopsy alone without full resection, cranial CT may be used instead of MRI, provided preoperative MRI completed within 14 days of biopsy.
G: TTF must start within 7 days of Day 1 and preferably a few days prior to beginning RT. TMZ must start within 7 days after beginning of RT. RT should be initiated no more than 14 days after Day 1.
H: To include scalp exam.
I: To include date of birth, gender, race, ethnicity, and education level.
J: Documentation of seizure frequency along with type of seizure (generalized or partial) and/or headache severity and frequency.
K: Including neurological exam, skin exam, and scalp assessment.
L: Obtained via chart review and by telephone (as needed) every 6 months until study completion.
M: To include history of prior treatments and any residual toxicity relating to prior treatment.
N: To include documentation of attribution, grade of toxicity, and if there is apparent correlation with the ceramic disc or adhesive gel on the transducer arrays.
O: With imaging assessment, status and extent of measurable disease on imaging. Repeat MRI every 2-3 months recommended.
P: Including clinical response or deterioration.
Q: Vitals to include: weight, temperature, pulse, respiration rate, and resting blood pressure.
R: MGMT methylation status and IDH mutation status must be assessed at the study site or patient's referral center. MGMT status will be used for stratification purposes but will not exclude patients from this study if they are either methylated, unmethylated, or indeterminate, or in process at the time of enrollment. Similarly, subjects with tumors that are IDH mutated or wildtype are both eligible. If results of MGMT and/or IDH are in process at time of screening, review at each subsequent visit until resulted.
S: To include alkaline phosphatase, ALT, AST, total bilirubin, calcium, blood urea nitrogen (BUN), creatinine, total protein, albumin, fasting glucose, potassium, sodium, chloride, bicarbonate.
T: To include PT, PTT, and INR.
U: If completed for screening within 14 days of Day 1, does not need to be repeated.
V: Cycle 1 day 1 dose is 150mg/m ² /day, all other cycles dose is 200mg/m ² /day.
W: To be collected and read by cardiology department.
X: To be done at Day 22 and Day 43 only.

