Y: Day 1 of the first 2 cycles of adjuvant therapy will fall within the DLT window with continued skin exams (Cycle 1 Day 1 and Cycle 2 Day 1). The subsequent cycles with post-TMZ maintenance TTField therapy will proceed per the standard of care (minimum of 6 cycles, up to 2 years). For continued participation in the trial, patients must continue to follow up every 2-3 months with a repeat MRI of the brain.
Z: To include PFS and OS.
AA: Monitor adverse events through 8 weeks post-RT/TMZ (through Day 1 of first cycle of Cycle 2).
BB: To be stopped post Day 43 visit on Day 49 (+ 7 days, if clinically appropriate).
CC: To be assessed if MRI completed per SOC since last review/contact.
DD: Time that must have elapsed prior to study enrollment (Day 1): 3-6 weeks (21-42 days) from time of definitive surgery or 2-4 weeks (14-28 days) from the time of biopsy for those who were only able to safely have a biopsy and not full resection.
EE: Use MRI from Day 1 Cycle 1 for assessment.
FF: To be completed monthly, may not be available at each visit.
GG: If indicated, per investigator discretion.
HH: Transducer arrays will need to be removed/replaced to complete.

**Please note, the above notations can be found in the body of the protocol, but are listed here as well with the intent of making the study calendar easier to follow.*

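### Long-term follow-up ties the recording of progression to a completed MRI, while the RANO table counts scan-free clinical decline as progression; sites may differ, and a literal reading biases PFS slightly upward

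*Combined protocol and SAP*

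**What the plan says.** **Follow-up rule.** Section 6, Maintenance TTField therapy (Long-Term Follow-up): "Investigators at each site will document the date of confirmed progression on MRI scan and or death". The same sentence qualifies the disease assessment: "with clinical response or deterioration, when an MRI has been completed per standard care".

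**Calendar.** In Appendix 3 the disease-assessment row for long-term follow-up carries footnotes P and CC. P reads "Including clinical response or deterioration" and CC reads "To be assessed if MRI completed per SOC since last review/contact". Read together, they make the assessment of deterioration conditional on a scan.

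**Definition of progression.** The RANO table in Section 7b makes any one of several criteria sufficient. Two need no scan: "clear clinical deterioration not attributable to other causes apart from the tumor" and "failure to return for evaluation as a result of death or deteriorating condition".

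**Analysis.** Section 8 plans Kaplan-Meier estimates of PFS at 6 months and 2 years. It defines no PFS event, event date or censoring rule.

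**The concern.** The collection rule is narrower than the definition it is meant to serve. Take a patient who declines at month 4.5, goes to supportive care without another MRI and dies at month 7. Under Section 7b this patient progressed at 4.5 months and is a PFS6 failure. Under the literal follow-up rule no progression is on record. Either PFS is 7 months and the patient counts as a PFS6 success, or the patient is censored at the last scan.

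The patients affected are those too ill to be scanned, so the error runs in one direction and a confidence interval does not reflect it. Section 6 presents the secondary endpoints as groundwork for later efficacy trials, where PFS6 may be set beside external figures that use full RANO progression.

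**Working it through.** The plan states no figure on this point to reproduce. The check is a comparison of text, calendar arithmetic and an illustration of size.

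**1. Is there another scan-free route?** The pseudoprogression rule in Section 7b deals with neurological decline only in a subject whose scan already raises concern. The removal criteria in Section 6 list neurological decline under safety, separately from progression, so a scan-free decline could be coded as a safety discontinuation. Neither supplies the missing route. Three other provisions do leave room for one; they are weighed under the objection.

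**2. When does the rule start?** Cycle 1 Day 1 is Study Day 78 and Cycle 2 Day 1 is Day 106. With 28-day cycles:
- Cycle 3 Day 1 = 106 + 28 = Day 134
- Cycle 5 Day 1 = 134 + 56 = Day 190
- Cycle 6 Day 28 = 78 + 6 × 28 − 1 = Day 245, so maintenance starts at about Day 246

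Counting from Day 1 (the plan does not state the PFS time origin), 6 months is about Day 183. The calendar places CC on cycles 3-6 and on maintenance, so the condition is in force from about Day 134, before the PFS6 landmark. The decline at month 4.5 (about Day 137) falls in cycle 3.

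**3. Size, death route.** Let true PFS be exponential with rate λ = ln 2 / (median PFS) and time from decline to death exponential with rate μ = ln 2 / (median decline-to-death). Let q be the share of progressions that are scan-free and s the month at which the rule starts. For t > s the reported curve is

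S_rep(t) = e^(−λt) + q · [λ/(μ−λ)] · [e^(−λt) − e^(−μt) · e^((μ−λ)s)]

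The second term is the share of patients who have progressed without a scan since s and are still alive at t.

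Central case, not from the documents: median PFS 9 months, q = 20%, median decline-to-death 2 months, s = 134/30.44 = 4.40.
- λ = 0.0770, μ = 0.3466, λ/(μ−λ) = 0.2857
- e^(−6λ) = 0.630; e^(−6μ) · e^((μ−λ)s) = 0.125 × 3.276 = 0.410
- Added term = 0.20 × 0.2857 × (0.630 − 0.410) = 0.0126
- PFS6 goes from 63.0% to 64.3%. Setting S_rep = 0.5 gives a median of about 9.5 months instead of 9.0.

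Over median PFS 7/9/11 months, q 10/20/30% and decline-to-death 1/2/3 months:

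| Rule applies from | PFS6 overstated by (points) | Central | Median PFS overstated by (months) | Central |
|---|---|---|---|---|
| Day 134 (calendar) | 0.4 to 2.4 | 1.3 | 0.1 to 1.3 | 0.5 |
| Day 246 (maintenance only) | 0 | 0 | 0 to 0.8 | 0.2 |

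**4. Size, censoring route.** A separate simulation censored scan-free decliners at a last MRI up to 2.5 months before decline. It used median PFS 5-9 months, 5-30% of progressions scan-free and a start at Day 106. PFS6 rose by about 0.5-4.3 points and median PFS by about 0.1-2.1 months. The grid differs and the start is earlier than Day 134, so these figures show direction and order of size and are not directly comparable with the table.

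**5. Scale.** The 95% half-width for a proportion of 0.55 with n = 30 is 1.96 × √(0.55 × 0.45 / 30) = 17.8 points. A shift of 1.3 points is 0.013 × 30 ≈ 0.4 of a patient.

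**The case against.** The strongest reply is that the plan does not close off clinical progression. The long-term follow-up text refers the reader to the response section for its criteria, and so to the RANO table. It has coordinators collect disease progression from records at least every 6 months, with no MRI condition. The calendar's survival row lists PFS under footnote Z, and CC is not on that row. All of this stands. A reader might infer that progression can be recorded only from an MRI; the documents support the weaker statement that they give sites two incompatible instructions.

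A reader might also infer that a patient who stops scanning stays progression-free until death. The plan does not settle that. Section 6 makes an MRI every 2-3 months a condition of continued participation after cycle 2, although the maintenance text only recommends scans. Such a patient could equally be censored. Under the death route the event is delayed, not lost.

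The sentence with the MRI wording sits in the maintenance phase, after the PFS6 landmark. Only the calendar carries the condition into cycles 3-6, through a cell that spans both phases in a table damaged in extraction. If the condition is confined to maintenance, PFS6 is unaffected. A reader who applied the rule from Day 1 would get an overstatement of about 0.7-6.8 points. The documents do not support that start, because the condition belongs to long-term follow-up.

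Finally, Section 6 says that the secondary endpoints are not powered, and there is no comparator arm. That limits the consequence but does not remove the contradiction.

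**Conclusion.** The contradiction holds: the follow-up rule and footnotes P and CC make clinical deterioration depend on a scan, and the RANO table does not. Because other text points the other way, the likely result is different practice between sites, with upward bias in PFS wherever the rule is followed literally, whether by dating the event at death or by informative censoring.

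The size is modest. By the death route from about Day 134, PFS6 is overstated by about 0.4-2.4 points (central 1.3) and median PFS by about 0.1-1.3 months (central 0.5). If only the maintenance phase is affected, PFS6 does not change and median PFS rises by 0-0.8 months. These figures rest on exponential times and on scan-free shares and decline-to-death times for which the documents give no source. They are well inside the sampling error at n = 30, and the primary safety endpoints are untouched. The change is still worth making, because the bias is one-sided and cheap to remove.

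**What to change.** - **Section 6, long-term follow-up, and Appendix 3 footnote CC:** limit the MRI condition to objective response and extent of measurable disease.
- **Every chart review or contact:** record the date and basis of progression by any criterion in the Section 7b table, whether or not an MRI was done.
- **Section 8:** define the PFS event as the earliest of MRI progression, clinical progression (including failure to return because of decline) and death. State that stopping scans because of decline is an event and not a censoring, and state how other patients without a scan are censored.

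The cost is wording and one date-and-reason field on the case report form, completed at reviews that already take place. No extra visits or scans are needed. Dating clinical progression will need some investigator judgment, and recording the basis lets a reader see how many events depend on it.

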7. SUBJECT ASSESSMENTS FOR SAFETY AND EFFICACY

The study procedure calendar for this study is provided in **Appendix 3**.

a) Evaluation of Safety and Tolerability**Dose Limiting Toxicity**

Dose limiting toxicities (DLTs) are defined as any severe or life-threatening treatment-related toxicity that precludes the use of a specified dose of any of the study treatments (TTFields, temozolomide, radiation) including continued use of Optune TTFields device at the standard treatment levels and schedule set out by prior studies. This study will prioritize preserving the standard of care for glioblastoma using approved dosing and radiation of temozolomide and radiation.

Toxicities will be graded according to the CTCAE (Version 5.0) scale. If multiple toxicities are seen, the presence of DLT should be based on the most severe toxicity experienced. Dose-limiting toxicities will be defined as any of the following events which occur during the experimental trimodal therapy with TTFields is added concurrently to radiation and temozolomide therapy or during the 8 weeks after RT is completed, and are considered by the investigator to be attributable to TTFields or the combination of TTFields with radiation and/or temozolomide:

- Any Grade > 3 thrombocytopenia, and Grade 4 anemia and neutropenia.
- Any nonhematologic Grade > 3 toxicity (including nausea, vomiting, or diarrhea), excluding alopecia.

- Any Grade 3-4 radiation-induced skin changes that persist for greater than 7 days and does not improve with management recommendations as outlined in toxicity management.
- Any adverse effect deemed by the investigator, patient's primary neuro-oncologist, or radiation oncologist to be life threatening in nature.

In the event of a dose-limiting toxicity, the subject will be discontinued from treatment and followed for toxicity assessment and management and a joint decision will be made by the investigator and sponsor whether to adjust the dose or schedule for other subjects or permanently close the study for safety. In the event that more than 33% of subjects experience a DLT, the study cannot continue unless a modification is made to the level of the particular treatment to which that adverse event is definitely attributable. As preliminary safety stops, the study will include two safety lead-ins receiving TTFields with concurrent chemoradiation. These initial 6 and then 15 subjects will undergo interim analyses after completion of chemoradiation to determine if the expanded cohorts should be permitted enrollment as planned or if a dose reduction in TTFields of 50% of the scheduled use is warranted for safety.

Subjects will continue to receive study treatment until confirmed tumor progression, unacceptable toxicity, or other discontinuation criteria as described; subjects MUST discontinue investigational product (and non-investigational product at the discretion of the investigator) if they meet criteria for removal from study therapy as referenced in that section.

Toxicity related to TTFields treatment: Treatment-related adverse events (TRAEs) and severe treatment-related adverse events (STRAEs) will be assessed in the following ways.

- Patients will be evaluated by a neuro-oncologist or radiation oncologist for potential skin toxicity from TTFields therapy. Routine skin care recommendations will be provided, including use clobetasol cream prior to electrode placement and adjusting array placement to avoid continued site irritation. If there are concerns by investigator, the subject will be referred to a dermatologist for specialized evaluation. Neurological and general physical evaluations as well as laboratory assessments will also be conducted by a neuro-oncologist or radiation oncologist to identify other potential toxicities.
- In addition to clinic visits and interventions, Patients will also be supported by a technician from Novocure for device troubleshooting and compliance checks.
- All other adverse effects, either mild, or serious, will be triaged by a physician in coordination with the primary investigators of the study.
- All adverse events, whether minor or serious will be reported according to protocol guidelines (see Reporting of adverse events).

b) Evaluation of Response

Patients will be evaluated for response using the Response Assessment in Neuro-Oncology (RANO) criteria³². Subjects who have lesions equal or less than 1cm on baseline will only be followed for assessment of progressive (PD) or stable disease (SD). SD will be marked by

the lack of observable progression on MRI. PD will be marked by any growth or recurrence of lesions consistent with tumor on MRI based on RANO criteria as follows:

Table #: RANO criteria for Response Assessment Incorporating MRI and Clinical Factors ³²	
Response	Criteria
Complete Response	Requires all of the following: complete disappearance of all enhancing measurable and nonmeasurable disease sustained for at least 4 weeks; no new lesions; stable or improved nonenhancing (T2/FLAIR) lesions; subjects must be off corticosteroids (or on physiologic replacement doses only); and stable or improved clinically. Note: subjects with nonmeasurable disease only cannot have a complete response; the best response possible is stable disease.
Partial Response	Requires all of the following: 50% or greater decrease compared with baseline in the sum of products of perpendicular diameters of all measurable enhancing lesions sustained for at least 4 weeks; no progression of nonmeasurable disease; no new lesions; stable or improved nonenhancing (T2/FLAIR) lesions on same or lower dose of corticosteroids compared with baseline scan; the corticosteroid dose at the time of the scan evaluation should be no greater than the dose at time of baseline scan; and stable or improved clinically. Note: Subjects with nonmeasurable disease only cannot have a partial response; the best response possible is stable disease.
Stable Disease	Requires all of the following: does not qualify for complete response, partial response, or progression; stable nonenhancing (T2/FLAIR) lesions on same or lower dose of corticosteroids compared with baseline scan. In the event that the corticosteroid dose was increased for new symptoms and signs without confirmation of disease progression on neuroimaging, and subsequent follow-up imaging shows that this increase in corticosteroids was required because of disease progression, the last scan considered to show stable disease will be the scan obtained when the corticosteroid dose was equivalent to the baseline dose.
Progression	Defined by any of the following: Greater than or equal to 25% increase in sum of the products of perpendicular diameters of enhancing lesions compared with the smallest tumor measurement obtained either at baseline (if no decrease) or best response, on stable or increasing doses of corticosteroids*; significant increase in T2/FLAIR nonenhancing lesions on stable or increasing doses of corticosteroids compared with baseline scan or best response after

	initiation of therapy* not cause by comorbid events (eg, radiation therapy, demyelination, ischemic injury, infection, seizures, post-operative changes, or other treatment effects); any new lesion; clear clinical deterioration not attributable to other causes apart from the tumor (eg, seizures, medication adverse effects, complications of therapy, cerebrovascular events, infection, and so on) or changes in corticosteroid dose; failure to return for evaluation as a result of death or deteriorating condition; or clear progression of non-measurable disease.
--	--

Evaluation of Pseudoprogression

Pseudoprogression is defined as worsening of the MRI lesions (enhancing lesion, T2/FLAIR hyperintense nonenhancing lesions) as a result of effects other than tumor growth. These can be the result of treatment effects from radiation, TTFields therapy, or chemotherapy, or changes in the steroid dose. Pseudoprogression is typically self-limited and suggests different clinical implications from true progression of the brain tumor. However, clinically and radiographically, pseudoprogression and tumor progression are difficult to distinguish.

MRIs in this study will be evaluated centrally by the principal investigator according to RANO criteria and definitions and need to account for possible pseudoprogression from any of the treatments. Therefore, in this trial, if a subject has an MRI scan concerning for progression without substantial neurological symptoms or signs within 6 months of starting TTFields therapy, it is recommended that the subject continue therapy and obtain a follow-up scan approximately 4 weeks apart to confirm progression. If that follow-up scan confirms progression, the patient shall be taken off the study treatments. If that scan is stable when compared to the prior scan, then pseudoprogression will be noted and treatment will continue. If a subject whose scan is concerning for progression also develops substantial neurological decline, or requires increasing steroid dose beyond the daily limit of 8mg dexamethasone for more than 4 weeks, then no confirmatory scan is needed; progression will be noted and that subject shall be discontinued from the study treatments. Similarly, no confirmatory scan is needed if a subject develops MRI changes concerning for progression with or without substantial neurological decline after 6 months of initiating TTFields therapy.

Reporting of Adverse Events

Evaluation of Safety

Analyses will be performed for all patients having received at least one day of TTFields therapy. The study will use the CTCAE v5.0 for reporting of non-hematologic adverse events and modified criteria for hematologic adverse events, see Section 7a (Subject assessments for evaluation of safety and tolerability).

There will not be a formal Study Chair. There will be three DSMC members who will share the responsibility of monitoring study conduct and safety across participating sites.

Definitions of Adverse Events

Adverse Event

An adverse event (also known as an adverse experience) is defined as any untoward medical occurrence associated with the use of a medical device in humans, whether or not considered device related. More specifically, an adverse event (can be any unfavorable and unintended sign (e.g., an abnormal laboratory finding), symptom, or disease temporally associated with the use of a device, without any judgment about causality. An adverse event can arise from any use of the device (e.g., off-label use, use in combination with another treatment or drug).

Adverse reaction

An adverse reaction is defined as any adverse event caused by the use of a medical device. Adverse reactions are a subset of all suspected adverse reactions for which there is reason to conclude that the device use caused the event.

Suspected

A suspected adverse reaction is defined as any adverse event for which there is a reasonable possibility that the use of the device caused the adverse event. For the purposes of IDE safety reporting, “reasonable possibility” indicates that there is evidence to suggest a causal relationship between the device use and the adverse event. A suspected adverse reaction implies a lesser degree of certainty about causality than an adverse reaction.

Unexpected

An adverse event or suspected adverse reaction is considered *unexpected* if it is not listed in the investigator brochure or package insert(s), or is not listed at the specificity or severity that has been observed, or, if an investigator brochure is not required or available, is not consistent with the risk information described in the general investigational plan or elsewhere in the current application.

Adverse events that would be anticipated to occur as part of the disease process are considered *unexpected* for the purposes of reporting because they would not be listed in the investigator brochure. For example, a certain number of non-acute deaths in a cancer trial would be anticipated as an outcome of the underlying disease, but such deaths would generally not be listed as a suspected adverse reaction in the investigator brochure.

Serious

An adverse event or suspected adverse reaction is considered *serious* if, in the view of either the investigator or sponsor, it results in any of the following outcomes:

- Death
- Life-threatening adverse event
- Inpatient hospitalization or prolongation of existing hospitalization
- A persistent or significant incapacity or substantial disruption of the ability to conduct normal life function
- Congenital anomaly/birth defect

Important medical events that may not result in death, are life-threatening, or require hospitalization may be considered serious when, based upon appropriate medical judgment, they may jeopardize the patient or subject and may require medical or surgical intervention to

prevent one of the outcomes listed in this definition. Examples of such medical events include allergic bronchospasm requiring intensive treatment in an emergency room or at home, blood dyscrasias or convulsions that do not result in inpatient hospitalization, or the development of drug dependency or drug abuse.

Life-threatening

An adverse event or suspected adverse reaction is considered *life-threatening* if, in the view of either the investigator or sponsor, its occurrence places the patient or subject at immediate risk of death. It does not include an adverse event or suspected adverse reaction that, had it occurred in a more severe form, might have caused death.

Recording of an Adverse Event

All grade 3 and above adverse events will be entered into the CTMS, Velos, whether or not the event is believed to be associated with use of the study device. Data about these events and their severity will be recorded using the NCI CTCAE v5.0.

All SAEs will be reviewed by a DSMC, which will consist of a panel of experts in oncology, neuro-oncology, biostatistics, or radiation oncology who are not direct investigators in this study. The PI will identify members of the DSMC and receive feedback and recommendations from the DSMC as to the safety of continuing the trial. The PI and study manager will be responsible for facilitating the proceedings as non-committee members. The committee will meet twice a year, or more if needed.

The Investigator will assess all adverse events, assign attribution of the possible association of the event with use of the investigational device, and this information will be entered into CTMS (Velos) using the classification system listed below:

Relationship	Attribution	Description
Unrelated to investigational drug/intervention	Unrelated	The AE is clearly NOT related to the intervention
	Unlikely	The AE is doubtfully related to the intervention
Related to investigational drug/intervention	Possible	The AE may be related to the intervention
	Probable	The AE is likely related to the intervention
	Definite	The AE is clearly related to the intervention

A more detailed definition of possible attributions is denoted in the following table:

Unrelated:	The event is clearly related to an event that may be due to environmental or accidental occurrence or other factors such as the subject's clinical state, therapeutic interventions, or concomitant drugs administered to the subject.
------------	--

Unlikely	The event is most likely produced by other factors such as the subject's clinical condition, therapeutic interventions, or concomitant drugs administered to the subject, and does not follow a known response pattern to the study drug or device.
Possible	The event follows a reasonable temporal sequence from the time of drug administration or use of device, and/or follows a known response pattern to the study drug or device, but could have been produced by other factors such as the subject's clinical condition, therapeutic interventions, or concomitant drugs administered to the subject.
Probable	The event follows a reasonable temporal sequence from the time of drug administration or use of device, and follows a known response pattern to the study drug or device, and cannot be reasonably explained by other factors such as the subject's clinical condition, therapeutic interventions, or concomitant drugs administered to the subject.
Definite	The event follows a reasonable temporal sequence from the time of drug administration or use of device, and follows a known response pattern to the study drug or device, and cannot be reasonably explained by other factors such as the subject's clinical condition, therapeutic interventions, or concomitant drugs administered to the subject, and either occurs immediately following study drug administration or use of device or improves on stopping the study drug or device, or reappears on repeat exposure

The relationship of the adverse event to the study treatment must be specified using the following definitions:

Signs or symptoms reported as adverse events will be graded and recorded by the Investigator according to the CTCAE. When specific adverse events are not listed in the CTCAE they will be graded by the Investigator as *none*, *mild*, *moderate* or *severe* according to the following grades and definitions:

- Grade 0 No AE (or within normal limits)
- Grade 1 Mild; asymptomatic or mild symptoms; clinical or diagnostic observations only; intervention not indicated
- Grade 2 Moderate; minimal, local, or noninvasive intervention (e.g., packing, cautery) indicated; limiting age-appropriate instrumental activities of daily living (ADL)
- Grade 3: Severe or medically significant but not immediately life-threatening; hospitalization or prolongation of hospitalization indicated; disabling; limiting self-care ADL
- Grade 4: Life-threatening consequences; urgent intervention indicated
- Grade 5: Death related to AE

Follow-up of Adverse Events

All adverse events will be followed with appropriate medical management until resolved. Patients discontinued from study therapy for unacceptable adverse events will be followed until resolution or stabilization of the adverse event and to the end of the study. For selected adverse events for which administration of the investigational device was stopped, a re-challenge of the subject with the investigational device may be conducted if considered both safe and ethical by the Investigator.

Adverse Events Monitoring

The Principal Investigator will review all adverse events and determine reportability to the DSMC and Providence's Institutional Review Board (IRB) per IRBAE reporting criteria; and, when the study is conducted under an Investigational Device Exemption (IDE), to the Food and Drug Administration (FDA) if it meets the FDA reporting criteria.

After the first 6 patients complete the lead-in phase, a written report will be submitted to the DSMC members describing the cohort, adverse events, and any Dose Limiting Toxicities observed, in accordance with the protocol. The report will be reviewed by the DSMC. Approval for the expansion cohort must be obtained from the DSMC prior to implementation.

Expedited Reporting

Reporting to the Data and Safety Monitoring Board

If a death occurs during the treatment phase of the study or within 30 days after the last administration of the study device and it is determined to be related either to the study device or to a study procedure, the Investigator or his/her designee must notify the PI, [name], or designee, Regulatory Manager, [name], within 1 business day of knowledge of the event. The contact may be by phone or e-mail. Death due to disease progression need not be reported to the PI or designee.

Reporting to Institutional Review Board

The Principal Investigator must report events meeting the IRB definition of "Unanticipated Problem" (UP) within 5 business days of his/her awareness of the event.

Expedited Reporting to the Food and Drug Administration

If the study is being conducted under an IDE, the Sponsor-Investigator is responsible for determining whether or not the suspected adverse reaction meets the criteria for expedited reporting in accordance with Federal Regulations (21 CFR §312.32).

The Investigator must report in an IDE safety report any suspected adverse reaction that is both serious and unexpected. The Sponsor-Investigator needs to ensure that the event meets all three definitions:

- Suspected adverse reaction
- Unexpected
- Serious

Serious and unexpected AEs must be reported by the investigator to Providence Regional Research Regulatory Office and the Study Manager by email at [contact] and [contact] or fax to [contact] and [contact] within 24 hours of the investigator's knowledge of the event. Providence will also report the SAEs to the FDA.

If the adverse event does not meet all three of the definitions, it should not be submitted as an expedited IDE safety report.

The timeline for submitting an IDE safety report to FDA is no later than **15 calendar days** after the Investigator determines that the suspected adverse reaction qualifies for reporting (21 CFR 312.32(c)(1)). MedWatch 3500A (Mandatory Reporting) form is available at: <https://www.fda.gov/Safety/MedWatch/HowToReport/DownloadForms/default.htm>

Any unexpected fatal or life-threatening suspected adverse reaction will be reported to FDA no later than **7 calendar days** after the Investigator's initial receipt of the information (21 CFR 312.32(c)(2)).

Any relevant additional information that pertains to a previously submitted IDE safety report will be submitted to FDA as a Follow-up IDE Safety Report without delay, as soon as the information is available (21 CFR 312.32(d)(2)).

